Clinical Development

INC424/ruxolitinib/Jakavi®

REALISE (CINC424A2411) / NCT02966353

A multicenter phase II, open label, single arm study to evaluate the efficacy and safety of Ruxolitinib in the treatment of anemic myelofibrosis patients.

Statistical Analysis Plan (SAP) Amendment 1

Author: Trial Statistician, [REDACTED]

Document type: SAP Documentation

Document status: Final

Release date: 12-Mar-2019

Number of pages: 29

Property of Novartis

For business use only

May not be used, divulged, published or otherwise disclosed
without the consent of Novartis

Document History – Changes compared to previous final version of SAP

Date	Time point	Reason for update	Outcome for update	Section and title impacted (Current)
12 Mar 2019	Before DBL	To modify windowing rules	Analysis table modified to exclude EOT in visit window	Section 2.1.1
		To remove text	Removed text for “Significant non-drug therapies” as it is not captured in the study	Section 2.4.2
		To add Spleen response definition and analysis by IWG-MRT criteria and also to add an analysis for primary endpoint at any time during the study.	Add definition and analysis of spleen response as per IWG MRT Criteria as per the recommendation from steering committee	Section 2.5.4
		To add an analysis on transfusion requirements and modify some text	Added clarification that unit of blood transfusion will be used for analysis and not the episode of transfusion; An analysis for transfusion dependent rate added for patient who were not TD at baseline	Section 2.7.2
		To add some decription on Adverse Event of Specail Interest (AESI)	Add a breif discription on AESI and a listing is proposed for AESI	Section 2.8.1.1
		To remove analysis	Shift tables based on low/normal/high ranges removed	Section 2.8.3
		To remove analysis	Shift table for baseline ECOG score vs worst post-baseline ECOG score removed. ECOG score over time will only be listed	Section 2.8.4.2
		To add description of PRO related derivations and few analysis	Added analysis on PRO similar to spleen response at Week 24	Section 2.11

Date	Time point	Reason for update	Outcome for update	Section and title impacted (Current)
		To add description of DIPSS score calculation	Added definition and criteria to calculate DIPSS risk scores and risk groups	Section 5

Table of contents

Table of contents	4
List of abbreviations	6
1 Introduction	8
1.1 Study design.....	8
1.2 Study objectives and endpoints	8
2 Statistical methods.....	9

LCM	Lower Costal Margin
MedDRA	Medical Dictionary for Drug Regulatory Affairs
MF-7	Myelofibrosis 7 Item Symptom Scale
MFSAF	Myelofibrosis Symptom Assessment Form
NR	Not reached
PD	Pharmacodynamic
NCI	National Cancer Institute
PDI	Planned Dose Intensity
PET-MF	Post-Essential Thrombocythemia Myelofibrosis
PGIC	Patient Global Impression of Change
PK	Pharmacokinetics
PMF	Primary Myelofibrosis
PPV-MF	Post-Polyctyhemia Vera-Myelofibrosis
PT	Preferred Term
PPS	Per-Protocol Set
PRO	Patient-reported Outcomes
RDI	Relative Dose Intensity
SAE	Serious Adverse Event
TBIL	Total Bilirubin
TD	Transfusion Dependent
SAP	Statistical Analysis Plan
SOC	System Organ Class
TFLs	Tables, Figures, Listings
TD	Transfusion Dependent

TI Transfusion Independent
ULN Upper Limit of Normal
WBC White Blood Cell

1 Introduction

This SAP describes the detailed statistical methodology of the study CINC424A2411: A Phase II study designed to assess the efficacy and safety of ruxolitinib in patients with Primary Myelofibrosis (PMF), Post-Polycythemia Vera-Myelofibrosis (PPV-MF), or Post-Essential Thrombocythemia Myelofibrosis (PET-MF).

Data will be analyzed by Novartis according to the Data analysis Section 10 of the study protocol which is available in Appendix 16.1.1 of the clinical study report. Important information is given in the following sections and details are provided, as applicable, in Appendix 16.1.9 of the clinical study report.

1.1 Study design

This is a multicenter phase II, open label, single arm study to assess the efficacy and safety of ruxolitinib in patients with Primary Myelofibrosis (PMF), Post-Polycythemia Vera-Myelofibrosis (PPV-MF), or Post-Essential Thrombocythemia Myelofibrosis (PET-MF) who have splenomegaly that is equal to or greater than 5 cm below the left costal margin and with anemia defined by Hb less than 10 g/dL.

The target number of patients for this trial is 50. The primary analysis will be performed when all enrolled patients have completed the Week 24 visit or have discontinued from the study prior to Week 24.

No interim analysis is planned for this study.

1.2 Study objectives and endpoints

Objectives and related endpoints are described in Table 1-1 below:

Table 1-1 Objectives and related endpoints

Objective	Endpoint
Primary	
To determine the spleen length response rate at Week 24.	Proportion of patients achieving a 50% reduction in spleen length at Week 24
Secondary	
To evaluate safety.	Safety will be assessed by Frequency and severity of adverse events and serious adverse events and AEs leading to discontinuations. Changes in hematology/biochemistry parameters over time.
To determine the spleen length response rate at Week 48.	Proportion of patients achieving a 50% reduction in spleen length at Week 48.

To evaluate the effect of ruxolitinib on spleen length.	Percent change from baseline in spleen length over time.
To evaluate the effect of ruxolitinib on symptoms.	Summary of the Modified MFSAF v2.0 and MF-7 over time.
To evaluate the effect of ruxolitinib on Patient Global Impression of Change (PGIC).	PGIC at each visit where measured.
To evaluate the effect of ruxolitinib on transfusion requirements.	Summary of transfusions over time. For Transfusion Dependent (TD)* patients, the following will be analyzed: Transfusion independence (TI) rate (requiring no transfusion for ≥ 12 weeks at any time). Transfusion response rate (not TD: having 5 or less transfusion for ≥ 12 weeks at any time).

2 Statistical methods

2.1 Data analysis general information

With SAS® ver. 9.4 or higher, the analysis for this study will be conducted by statisticians and statistical programmers from Novartis or designated CRO after all patients have either completed or have been prematurely discontinued from the study.

Unless otherwise specified, qualitative data (e.g., gender) will be described using frequency and percentages, a missing category will be included as applicable; while quantitative data will be described using descriptive statistics: n, mean, standard deviation, median, minimum, and maximum.

Unless otherwise stated, summary tables/figures/listings will be on all patients included in the population under consideration.

All statistical analyses will be performed using all data collected in the database up to data cut-off date. Only data with an assessment date or event start date (e.g. vital sign assessment date or start date of an adverse event) prior to or on the cut-off date will be included in the analysis.

All the events with start dates before or on the cut-off date and end date after the cut-off date will be reported as 'continuing at the cut-off date'. The same rule will be applied to events starting before or on the cut-off date and not having documented end date. This approach applies, in particular, to adverse event and concomitant medication reports. For these events, the end date will not be imputed and therefore will appear as missing in listings.

The final analysis will occur at the end of the study. All available data from all patients will be analyzed and summarized in a final CSR.

2.1.1 General definitions

Study treatment

Study treatment for this study is "ruxolitinib".

Date of enrollment

In this study, the date of enrollment is the date first ICF is signed.

Date of the first/last administration of study treatment

Date of the first administration of study treatment is derived as the first date when a non-zero dose of study treatment is administered.

Date of the last administration of study treatment is derived as the last date when a non-zero dose of study treatment is administered.

Reference start date

Reference start date for this study will be defined as the date of the first administration of study treatment.

Study day

The study day for safety assessments (e.g. adverse event onset, laboratory abnormality occurrence, vital sign measurement, dose interruption etc.) will be calculated as the difference between the date of the event (onset date of an event, assessment date etc.) and the start of study treatment plus 1. The first day of study treatment is therefore study Day 1. Example: if start of study treatment is on 05-Jan-2014 and start date of an adverse event is on 09-Jan-2014 then the study day of the adverse event onset is 5. For safety assessments before start of study treatment, the study day is negative and derived by (date of event – start date of study treatment). For example: if start of study treatment is on 05-Jan-2014 and date of lab measurement is on 02-Jan-2014 then the study day of the laboratory abnormality is -3. Note, the day of start of study treatment is day 1, and the day before the date of first study treatment is day – 1, not day 0.

Units conversion

If duration is reported in weeks, duration in days will be divided by 7.

Baseline

Baseline is the result of an investigation describing the “true” state of the subject before start of study treatment administration.

The last available assessment on or before the date of start of study treatment (as defined in Section 2.1.3) is taken as “baseline” assessment. In case time of assessment and time of treatment start is captured, the last available assessment before the treatment start date/time is used for baseline.

On-treatment assessment/event and observation periods

The overall observation period will be divided into three mutually exclusive segments:

1. pre-treatment period: from day of subject’s first informed consent to the day before first administration of study treatment
2. on-treatment period: from date of first administration of study treatment to 30 days after date of last actual administration of any study treatment (including start and stop date)
3. post-treatment period: starting at day 30+1 after last administration of study treatment.

Safety summaries (tables, figures) include only data from the on-treatment period with the exception of baseline data which will also be summarized where appropriate (e.g. change from baseline summaries). In addition, a separate summary for death including on-treatment and post-treatment deaths will be provided. In particular, summary tables for adverse events (AEs) will summarize only on-treatment events, with a start date during the on-treatment period (treatment-emergent AEs).

However, all safety data (including those from the pre- and post-treatment period) will be listed and those collected during the post-treatment period will be flagged.

Analysis Visit Windows

In order to summarize data collected over time (including unscheduled visits), the assessments will be time slotted. The following general rule will be applied in creating the assessment windows: If more than one assessment is done within the same time window, the assessment performed closest to the target date will be used. If 2 assessments within a time window are equidistant from the target date, then the earlier of the 2 assessments will be used. If there are multiple assessments on the same date, then the worst case will be used. Data from all assessments (scheduled and unscheduled), including multiple assessments, will be listed.

Analysis Visit windows

Assessment	Target day of assessment	Time Interval
Baseline	1	≤ Day 1
Week 4	28	Day 2 to day 42
Week 8	56	Day 43 to day 70
Week 12	84	Day 71 to day 98
Week 16	112	Day 99 to day 126
Week 20	140	Day 127 to day 154

Week 24	168	Day 155 to day 210
Week 36	252	Day 211 to day 294
Week 36+(12*k)	d=k*84+252, k=1,2,3,etc.	Day d-41 to day d+42

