6.3.3 Dose interruption and discontinuation of study drug

In some circumstances, it may be necessary to temporarily interrupt treatment as a result of adverse drug reaction that may have an unclear relationship to study drug. Except in cases of emergency or for protocol mandated holds for ANC, hemoglobin or platelet count, it is

recommended that the investigator consult with the Sponsor medical monitor (or other representative of the Sponsor) before temporarily interrupting therapy.

Study drug may be held by the investigator at any time if there is concern about patient safety, and for all aspects of the conduct of the protocol the safety of the individual patient is paramount. Treating investigators may employ any means necessary to ensure patient safety, particularly in medical circumstances not anticipated by this protocol. Dosing must be halted immediately if any of the following occur:

- Platelet counts fall below 25,000/ μ L
- ANC levels fall below 500/ μ L
- Hemoglobin cannot be maintained ≥ 6.5 g/dL despite the use of transfusion therapy

Dosing may be reinstated following dose holding as detailed in [Section 6.3.6](#). In order to provide sufficient data to make the dose adjustment decisions, it is recommended that hematology parameters be obtained at least weekly for platelet count $< 100,000/\mu$ L or ANC $< 1000/\mu$ L and at least two times weekly for platelet count $< 50,000/\mu$ L or ANC $< 500/\mu$ L. (Note: patients with platelet counts of $< 10,000/\mu$ L should be hospitalized, unless local or national practice does not permit it).

If a patient on a dose-hold requires frequent testing for safety parameters, these tests may be performed at a local laboratory. If the study drug is interrupted for any reason for more than 8 weeks, dosing may not be restarted, except in the case of splenectomy, for which a maximum 12 week period of study drug interruption is permitted. Although study guidelines provide for dose reduction/interruption for the management of hematologic or non-hematologic toxicities that occur during the course of the study, the following guidelines should be used to determine whether permanent discontinuation of study drug is necessary.

6.3.4 Discontinuation of study drug for hematologic toxicity:

Study drug MUST be permanently discontinued if the lowest allowed dose (5 mg BID or 5 mg QD with concomitant CYP3A4 inhibitor) is not tolerated due to the following:

- Platelets cannot be maintained $\geq 25,000/\mu$ L.

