7.1.6 Follow up for safety evaluations

All patients must have safety evaluations for 30 days after the last dose of study treatment.

Data collected should be added to the Adverse Events CRF and the Concomitant Medications CRF.

Follow-up evaluations

The following evaluations will be performed within 30 days after the last dose of study treatment. The following procedures will be performed and all observations will be recorded in the eCRF:

- Review of concomitant medications.
- Review of transfusion history
- A complete physical examination will be performed, including body weight and measurement of spleen by palpation.
- Vital signs to be performed in a sitting position after 5 minutes of rest)
- Blood sampling for serum chemistry and hematology tests.
- Record adverse events.

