10.5.3 Safety objectives

10.5.3.1 Analysis set and grouping for the analyses

For all safety analyses, the safety set will be used, unless specified otherwise.

The overall observation period will be divided into three mutually exclusive segments:

1. pre-treatment period: from day of patient's informed consent to the day before first dose of study medication
2. on-treatment period: from day of first dose of study medication to 30 days after last dose of study medication
3. post-treatment period: starting at day 31 after last dose of study medication.

The safety summary tables will include only assessments collected within 30 days after study treatment discontinuation and assessments on or prior to the data cut-off date for ongoing patients, unless otherwise specified.

All data, regardless of the observation period, will be listed and assessments collected in the pre-treatment and post-treatment period will be flagged in all the listings.

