2.8.3 Laboratory data

The summaries will include all assessments available for the lab parameter collected no later than 30 days after the last study treatment administration date (see Section 2.1.1.3).

The following summaries will be produced for hematology and biochemistry laboratory data (by laboratory parameter):

- Changes from baseline in hematology/biochemistry parameters over time.
- Worst post-baseline CTC grade (regardless of the baseline status). Each subject will be counted only for the worst grade observed post-baseline.
- Shift tables using CTC grades to compare baseline to the worst on-treatment value
- .
- Trends of lab parameter values over time (baseline and selected on-treatment timepoints) should be displayed via boxplots based on time windows and corresponding tables displaying the statistics used for the box plots by the selected time points.

The following listings will be produced for the laboratory data:

- Listings of all laboratory data, with CTC grade and classification relative to the laboratory normal range. Lab data collected during the post-treatment period will be flagged.
- Listing of all CTC grade 3 or 4 laboratory toxicities

Liver function parameters

Liver function parameters of interest are total bilirubin (TBIL), ALT, AST and alkaline phosphatase (ALP).

The number (%) of subjects with worst post-baseline values will be summarized:

- ALT or AST > 3xULN
- ALT or AST > 5xULN
- ALT or AST > 8xULN
- ALT or AST > 10xULN
- ALT or AST > 20xULN
- TBL > 2xULN
- TBL > 3xULN
- ALT or AST > 3xULN & TBIL > 2xULN
- ALT or AST > 3xULN & TBIL > 2xULN & ALP < 2xULN (potential Hy's law)

Potential Hy's Law events are defined as those patients with a concurrent occurrence of AST or ALT > 3xULN and TBIL > 2xULN and ALP < 2xULN in the same assessment sample during the on-treatment period. Further medical review has to be conducted to assess potential confounding factors such as, liver metastases, liver function at baseline etc.

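### Safety tables stop 30 days after the last non-zero dose while holds may last 8 weeks, so findings from hold day 31 are tabulated only if the patient restarts

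*SAP*

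**What the plan says.** **The window.** SAP 2.1.1 gives the "on-treatment period: from date of first administration of study treatment to 30 days after date of last actual administration of any study treatment". The anchor is explicit: "Date of the last administration of study treatment is derived as the last date when a non-zero dose of study treatment is administered". A hold at zero dose therefore does not move it. What follows is the "post-treatment period: starting at day 30+1 after last administration of study treatment".

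**What the window controls.** Under SAP 2.1.1 safety tables and figures use on-treatment data, plus baseline, and AE tables select by start date. SAP 2.8.3 limits laboratory summaries to assessments "collected no later than 30 days after the last study treatment administration date". Post-treatment data are listed and flagged. Deaths after the window have their own summary (SAP 2.8.2).

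**How long a hold may last.** Protocol 6.3.3 states: "If the study drug is interrupted for any reason for more than 8 weeks, dosing may not be restarted". Splenectomy is an exception, "for which a maximum 12 week period of study drug interruption is permitted".

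**Related protocol wording.** Protocol 10.5.3.1 ends the on-treatment period 30 days after the last dose, but then says: "The safety summary tables will include only assessments collected within 30 days after study treatment discontinuation". It also admits data up to the cut-off for ongoing patients, which the SAP definition does not repeat. Protocol 7.1.6 says: "The following evaluations will be performed within 30 days after the last dose of study treatment".

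**The concern.** Two patients can have the same hold and the same new finding on hold day 40. If dosing later restarts, the finding lies before the new last dose and is tabulated. If dosing never restarts, it becomes post-treatment and is only listed. Inclusion thus depends on something that happens after the finding, and the patients left out include those whose counts never recovered.

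This touches a named endpoint. AEs leading to discontinuation are part of the secondary safety endpoint (Protocol Table 3-1, SAP Table 1-1), and SAP 2.8.1 restricts AE summaries to the on-treatment period. Under Protocol 8.1.1 a worsened event is entered again with a new start date, and the action taken is recorded per event. An infection, bleed or worsened event that starts on hold day 40 and causes permanent discontinuation would be absent from the discontinuation table. Better tolerability is the rationale for the lower starting dose, so the safety tables carry much of the trial's message. With 50 patients, one reclassified patient is 2 percentage points (1/50).

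**Working it through.** The plan gives no figure on this point, and nothing here depends on the sample-size tables. The check is date arithmetic.

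**Inputs**
- Window after the last non-zero dose: 30 days (SAP 2.1.1, 2.8.3).
- Longest hold with restart still allowed: 8 × 7 = 56 days (Protocol 6.3.3).
- Recommended blood counts during a hold: at least twice weekly at very low counts, weekly at moderately low ones (Protocol 6.3.3).
- Label discontinuation rates in phase 3 MF studies (Protocol Appendix 6, section 4.8): any AE 11.3%; anaemia 0.3%; thrombocytopenia 0.7%; neutropenia 0.3%.

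**Step 1: classify hold days.** Let h be days since the last non-zero dose.
- Dosing restarts: every h precedes the new last dose, so 56 of 56 days are on-treatment.
- Dosing never restarts: h = 1 to 30 is on-treatment and h = 31 to 56 is post-treatment. Outside the tables: 56 − 30 = 26 days, and 26/56 = 46%.
- The hold becomes permanent by day 30: no hold day is lost.

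**Step 2: laboratory samples in a full 8-week hold without restart.** At one sample every 3.5 days, 8 of 16 fall after day 30. At weekly sampling, 4 of 8 do.

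**Step 3: what can change in the tables.** Platelet and ANC holds are triggered below 25,000/µL and at about 500/µL (Protocol 6.3.1.1, 6.3.3). The label table places values below those limits in grade 4 under CTCAE v3.0; I assume v4.03 uses the same limits. Grade 5 is not used for laboratory values (SAP 5.3). A lower count later in the same cell line therefore rarely changes the worst-grade or shift table. The abnormality that forced the hold must be reported as an AE (Protocol 8.1.2.1) and starts before the hold, so it stays in. What can be missed is:
- an AE that is new, or re-recorded as worse, after day 30;
- a new abnormality in another cell line or in liver values, and possibly a further haemoglobin grade;
- end-of-treatment (EOT) laboratory results, when EOT comes more than 30 days after the last dose. SAP 5.1.1 itself warns that the two dates can lie far apart.

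**Step 4: patients exposed.** The documents do not give the number of holds longer than 30 days, so this is an assumed range.
- Low: cytopenia-specific rates total at most 0.3 + 0.7 + 0.3 = 1.3%; 50 × 0.013 = 0.65 patients.
- High: every AE discontinuation follows a hold longer than 30 days; 50 × 0.113 = 5.65, about 6 patients.

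Both count patients to whom the rule could apply, not patients certain to lose an event from the tables.

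**The case against.** The case for leaving the rule alone is substantial.

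- **The window is a defensible prespecified choice.** Half-life is about 3 hours without appreciable accumulation (Protocol 1.2.1.2.1), and symptoms may return about a week after interruption (6.3.2). Events more than 30 days off drug are confounded by disease and later therapy. This stands, and it is why the present tables should remain.
- **Little disappears.** The triggering event stays in the AE tables, all deaths are summarised, all data are listed, and grade 3/4 laboratory values have a separate listing. This stands. A reader might infer that late-hold data are lost altogether, or that deep nadirs vanish from the grade tables. The documents do not support either reading.
- **Few patients may be affected.** Thrombocytopenia reversed within 1 to 3 weeks in the phase I/II study (Protocol 1.2.1.2.3), and the label gives a median of 14 days for platelet recovery. Eight weeks is a ceiling, and an investigator may stop earlier. This stands, although these patients all start anaemic and label rates may not transfer.
- **Protocol 10.5.3.1 may not contain two clocks.** The glossary defines discontinuation as the point when the patient permanently stops taking drug, which can be read as the last dose. The wording is unclear, but it is not a proven contradiction.

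None of this answers the central point: the same late-hold finding is tabulated or not according to a later restart, and no SAP rule covers a patient who never restarts.

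**Conclusion.** The concern holds in a limited form. For a hold that runs the full 8 weeks and becomes permanent, up to 26 of 56 hold days (46%) fall outside the safety tables; with a restart, none do. This applies to any hold without restart, not only to unresolved toxicity. The clearest consequence is that an AE causing permanent discontinuation can be missing from the table meant to count it. The number of patients is unknown: under 1 to about 6 of 50, on the label rates and the assumptions in the working.

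Three stronger readings are tempting but unsupported:
- The same arithmetic for a 12-week hold gives 54 of 84 days (64%), but that limit applies only to splenectomy, so it does not describe toxicity holds.
- A reader might infer that the summaries demonstrably favour the regimen. The selection could act that way, but the excluded days also contain off-drug recovery values, and the documents give no data on direction.
- A reader might treat the upper figure as an expected count. It requires every AE discontinuation to follow a hold longer than 30 days.

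The change is worth making because it is cheap, not because the trial's conclusions are shown to be at risk.

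**What to change.** In SAP 2.1.1, 2.8.1, 2.8.1.1 and 2.8.3, keep the tables based on last dose plus 30 days. Add a parallel version of the AE, AE-leading-to-discontinuation, AESI and laboratory summaries. For patients whose last dosing record is an interruption, the parallel version also counts data already collected up to the recorded date of permanent discontinuation (EOT), but not beyond death, withdrawal of consent or data cut-off. In the discontinuation table, count any AE recorded as leading to permanent discontinuation even if it starts after the 30-day limit.

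**Cost.** One added definition and one extra set of tables, from dates and data already collected. Some off-drug events unrelated to ruxolitinib will be counted, and the length of the added period will vary with when EOT is recorded. Showing both versions side by side makes the size of that effect visible.

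The sponsor should also reconcile Protocol 7.1.6 and 10.5.3.1 with the SAP, covering the reference date for the 30 days and the treatment of patients still on hold at a data cut-off. No follow-up schedule, hold rule or stopping rule is proposed here.
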